Table 6 outlines projected recruitment targets for both groups. Advanced testing will be offered to all participants to the cap in table 6, on the basis of fully informed consent. Progress in recruitment to both groups will be monitored by the project manager and monitor.

	F/F		F/M		F/G		TOTALS		S
	6-		6-		6-		6-		
Ages	11	12+	11	12+	11	12+	11	12+	All
ADVANCED	47	60	17	26	17	0	64	86	150
STANDARD	27	36	9	15	0	0	36	51	87

Total 74 96 26 41 17 0 117 137 254	Total	74	96	26	41	17	0	117	137	254	
------------------------------------	-------	----	----	----	----	----	---	-----	-----	-----	--

Table 6. Projected recruitment to standard and advanced testing arms for parent study.

Primary and Secondary Outcomes

The primary outcome measure for this study is the absolute change from base line values and CT scores.

The secondary outcome measures are as follows;

- height/weight/BMI
- FEV1
- Airway microbial culture
- Airway microbiome determination
- Nasal Lavage inflammatory markers
- Nasal microbiome determination
- Exhaled Nitric Oxide
- Liver function testing
- Liver ultrasound Liver
- Examination score
- Sputum inflammatory markers
- Sputum microbiome determination
- Stool inflammatory markers
- Stool microbiome determination
- Sweat Chloride
- Genetic modifiers of CF phenotype
- Abdominal symptom score
- CFQ-R
- Treatment Adherence
- Medication Pick up rates

Core Data to be Collected

Eligibility assessment

Prior to study enrolment, the investigator will assess subject eligibility. This will include reviewing the subject's current medication and medical history in detail to ensure no exclusion criteria are met and all inclusion criteria are met. As part of the eligibility assessment, a urine pregnancy test (CE marked) must be conducted in female participants considered of childbearing potential (WOCBP). WOCBP are defined as females that are fertile, following menarche, until becoming post-menopausal unless permanently sterile. Permanent sterilisation methods include hysterectomy, bilateral salpingectomy and bilateral oophorectomy. A postmenopausal state is defined as no menses for 12 months without an alternative medical cause. A negative test must be produced prior to enrolment and documented within the subject's medical records.

Demographic data

Core demographic data will be collected on all individuals including genotype, sex, date of birth, CF centre and medications.

Sweat Chloride

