The main foreseeable risk factor in this part of the study is the inability to collect a sputum specimen. Many patients, especially younger or healthier ones may not routinely produce sputum on a regular basis. We further suspect that, in light of the significant improvements in clinical outcomes demonstrated already for Kaftrio, that many individuals will go from being sputum producers to non-producers on treatment. We will work closely with the clinical teams to ensure that sputum specimens are optimized in terms of the split between laboratory and research processing. Each clinic has their own mechanism for trying to facilitate sputum production either at clinics or annual assessment – we will work with teams to ensure that saline induction, where used, can be facilitated by the research team to try to ensure a suitable sample sputum volume can be collected for all uses. We are aiming to collect 4 sputum samples over 2 years for RECOVER, with the baseline and year one samples prioritized. Where possible the research team will work with the subjects and clinical teams to ensure that all efforts are made to obtain a sufficient sample volume at these timepoints in particular, including sputum induction. The use of the TETRIS sputum processing protocol will mean that it is acceptable to use

P.I. [name] spontaneously produced and induced sputum interchangeably when obtaining samples. This will greatly facilitate optimal sampling.

We expect that an incomplete set of samples will be collected and have factored this into our study calculations in terms of numbers and budget. With a recruitment of 150 individuals to the advanced group we would ideally expect 600 sputum samples and 414 nasal lavage samples to process (1014 total). In reality we estimate that it is likely that we will have 90% of individuals produce one sputum sample, 80% to produce 2 samples, and 70% to produce 3 samples and 60% to produce 4 samples. We estimate that 80% of eligible individuals will produce one nasal lavage sample, 70% two samples and 60% three samples. The main foreseeable risk factor with nasal lavage is aspiration of isotonic saline. In practice this is a very similar procedure to sinus rinse which is commonly performed by many people with CF on a daily basis where we see almost no adverse effects in those who learn how to do the procedure. It is likely that some people may find this an uncomfortable or awkward procedure and elect not to do it.

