In this multi-centre longitudinal study of subjects starting on ETI we will be examining many different outcomes, and so sample size requirements are different for different aspects. Patients will be recruited to the study up to a cap of 254 participants. On the basis of the phase two trials of ETI(57), we are expecting a significant treatment effect in line with what was previously seen with Ivacaftor treatment in individuals with a gating mutation, and in excess of what was seen with Lumacaftor/Ivacaftor in individuals homozygous for F508del. Our sample size is higher than we expect to be required for most outcomes where data exists (see tables 11, 12, 13 below). We have aimed high deliberately for a number of reasons. Firstly, clinical research naturally carries risks in terms of adequacy of data collection. Secondly, we are keen to ensure that outcome measures can be cross referenced between each other and with previously collected, yet to be collected and data and samples. This will require excess power. With missing or incomplete samples across different outcome measures, complete datasets on a core number of individuals will necessitate collection in a larger cohort. Thirdly, this study represents a unique opportunity, which may not be replicated, to collect this data, and promises very significant insights into CF disease pathogenesis and response to therapies. In light of this, a large sample size with adequate sample collection we feel is important. Where data is available, we have performed sample size calculations (table 10). Where data is not available, we present a summary of key studies and evidence in the area.

Power and sample size calculations were produced for LCI as a main primary endpoint, using the GLMPOWER procedure in SAS 9.3 (Table11, Figure 5). A range of scenarios were considered for standard deviation from 2 (expected) to 3 (conservative) and power was computed for F/F participants only and for F/F and F/M participants combined. We estimated a conservative treatment effect at 1 unit of improvement in LCI (as seen with lumacaftor/ivacaftor), and an expected treatment effect at 2 unit of improvement in LCI (as seen with lvacaftor in gating mutations).

Group	Sample Size	Std Dev	Power (1 unit)	Power (2 unit)
F/F only	166	2	91.9%	99.4%
F/F & F/M	201	2	96.4%	99.9%
F/F only	166	2.5	76.6%	94.8%
F/F & F/M	201	2.5	85.3%	98.0%
F/F only	166	3	61.0%	84.7%
F/F & F/M	201	3	70.8%	91.7%

[figure not shown]

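### Table 6 lists 17 F/G children in the advanced row but leaves them out of its margins, so the advanced-testing cap is 150 by the stated total and 167 by the cells

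*Protocol*

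**What the plan says.** The Protocol section on advanced versus standard testing in the parent study gives the advanced group three additions to standard testing: spirometry-controlled CT, sputum collection and nasal lavage. Recruitment is set out in Table 6 by genotype and age. The text first describes the figures as projections for the two groups, and then uses the table as a limit: "Advanced testing will be offered to all participants to the cap in table 6, on the basis of fully informed consent".

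The columns of Table 6 are F/F 6-11, F/F 12+, F/M 6-11, F/M 12+, F/G 6-11 and F/G 12+, then the totals for 6-11, 12+ and all ages. The advanced row reads "ADVANCED 47 60 17 26 17 0 64 86 150". The standard row has F/F 27 (6-11) and 36 (12+), F/M 9 and 15, and no F/G participants, with totals of 36, 51 and 87. The Total row has F/F 74 and 96, F/M 26 and 41, and F/G 17 and 0, with totals of 117, 137 and 254.

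Two other sections rely on these figures. The sample size section for the parent study says: "Patients will be recruited to the study up to a cap of 254 participants". The section on risks in airway inflammation data collection says: "With a recruitment of 150 individuals to the advanced group we would ideally expect 600 sputum samples".

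**The concern.** The advanced total of 150, the standard total of 87 and the overall total of 254 cannot all be right, because 150 and 87 make 237. The advanced row shows 17 F/G children aged 6-11 that its own margins do not count.

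This matters because the table is used as a cap. The advanced arm is the parent study's source of CT scores, which the protocol names in its primary outcome, and of research sputum. If the cap has two values, so does the planned size of the CT and sputum samples. The number of children aged 6-11 who may be offered scans at baseline, year one and year two is also left open.

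**Working it through.** **Inputs.** All counts are from Table 6. The overall cap of 254 is also in the sample size section. The planning figures of 150 participants and 600 sputum samples are in the section on risks in airway inflammation data collection.

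**Margins that reproduce.**

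- Standard: 6-11 is 27 + 9 + 0 = 36; 12+ is 36 + 15 + 0 = 51; all is 36 + 51 = 87. All as stated.
- Columns, advanced plus standard: 47 + 27 = 74; 60 + 36 = 96; 17 + 9 = 26; 26 + 15 = 41; 17 + 0 = 17; 0 + 0 = 0. All as stated.
- Total row: 74 + 26 + 17 = 117; 96 + 41 + 0 = 137; 117 + 137 = 254. All as stated.
- Advanced 12+: 60 + 26 + 0 = 86. As stated.

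**Margins that do not reproduce.**

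| Quantity | From the cells | Stated |
|---|---|---|
| Advanced, 6-11 | 47 + 17 + 17 = 81 | 64 |
| Advanced, all ages | 81 + 86 = 167 | 150 |

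Adding the stated arm totals gives the same gap: 64 + 36 = 100 against 117 for ages 6-11, and 150 + 87 = 237 against 254 overall.

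**Source of the gap.** Leaving out the F/G cell gives 47 + 17 = 64 and 64 + 86 = 150, exactly the stated margins. Also, 254 - 237 = 17. The F/G column is counted in the Total row but not in the advanced margins, and nothing else is out of line.

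**Size.**

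- 17 / 150 = 11% of the stated advanced cap, and 17 / 254 = 7% of the study.
- CT: three parent-study scans per participant give 17 x 3 = 51 at most. The section on risks with CT data collection says many centres already scan every two years, and that only one extra scan per participant is then needed. If all 17 children attended such centres, the study-driven scans would number 17 x 1 = 17. The site mix is not given, so the range is 17 to 51.
- Sputum: 150 x 4 = 600 reproduces the planning figure; with 167 it would be 167 x 4 = 668. The multiplier of four is itself inconsistent with Table 14, which marks parent-study sputum at months 0, 6, 12, 18 and 24, five visits. At five, the figures would be 150 x 5 = 750 and 167 x 5 = 835.

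**The case against.** It can be said that these are projected targets, that the table does place the 17 children, and that only two margins are wrong. Much of that stands. The F/G 6-11 column shows 17 advanced and none standard, and the column total, the 117 and the 254 all agree with it. A reader might infer that sites cannot tell which arm these children belong to; the cells do say. What remains open is the size of the cap. The word projected does not settle it, because the next sentence treats the table as a limit and the sputum plan relies on 150.

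Broken table extraction is a fair question too, since the Total row is detached from the rest. It is an unlikely cause: every other margin and column reconciles, and the difference equals one cell.

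Three stronger inferences are not supported:

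- **Nasal lavage.** It is an advanced-arm procedure, so a reader might count it as affected. The nasal lavage section limits it to age 12 and over, and all 17 children are aged 6-11.
- **Power.** A reader might infer that the stated power is wrong. The LCI power table and Table 13 use n = 166 and n = 201, never 150 or 167, so the slip enters none of those figures. CT power at 150 or 167 would need a formula that the protocol does not give. One that approximates the Table 13 CT row gives 63.5% at n = 166, where the table states 62.0%, so it is not a sound basis.
- **Scan count.** Fifty-one extra scans is a ceiling, not an estimate, for the reason given in the working.

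**Conclusion.** Wrong as written. The advanced margins of 64 and 150 contradict the cells of their own row (81 and 167), and the stated arm totals fall 17 short of the 254 in the Total row and the sample size section. The advanced cap is therefore either 150 or 167. That changes by 17, or 11% of the stated cap, the number of children aged 6-11 who can be offered study CT and research sputum. In study-driven CT scans this is about 17 to 51, assuming all 17 children would take part and complete the schedule.

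The documents do not say which figure is intended. The cells and the 254 point to 167; the repeated 150 in the sputum plan points the other way. That the F/G column was simply missed when the advanced margins were summed is the plainest explanation, but it is an inference. The practical weight is modest: the error is definite and sits in an operating limit that feeds part of the primary outcome, but it alters no stated power figure.

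**What to change.** Reconcile the advanced row of Table 6 with its cells and with 254, in one of two ways:

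- If the cells and 254 stand, the advanced margins become 81 / 86 / 167, and 167 + 87 = 254.
- If 150 is the intended cap, move the 17 F/G children aged 6-11 to the standard row. Its margins become 36 + 17 = 53, 51 and 53 + 51 = 104, and 150 + 104 = 254.

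The sponsor must choose between them. State in the text which cap governs CT and sputum. Then bring the 150 and 600 in the section on risks in airway inflammation data collection into line, after reconciling its four samples per person with the five parent-study sputum visits in Table 14. The cost is a correction to one table row and a few dependent figures; no analysis or power calculation has to be redone.

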In healthy individuals, persistent or troublesome respiratory infection is prevented through the innate and adaptive immune function associated with normal airway epithelium and airway surface liquid, and the effectiveness of mucociliary clearance. In CF, defective CFTR activity leads to an abnormal airway surface liquid that is dehydrated (2) and has abnormal innate defence activity (3). Airway mucus is viscous and difficult to clear leading to mucus plugging. The physical and innate defence defects are associated with recurrent and/or persistent infection accompanied by significant airway inflammation, resulting ultimately in airway wall injury. Progressive inflammation over time is associated with the development of bronchiectasis (4), which is ultimately irreversible and leads to further impairment of airway clearance. The most common cause of death in people with CF is respiratory failure associated with progressive CF lung disease (5). CF lung disease starts in early infancy, and at school age more than 50% of children have bronchiectasis despite early diagnosis through screening and current standard treatments (6-9).

Markers of Airway Inflammation

Airway inflammation in CF is present from infancy, is disproportional to the infectious insult, persists and worsens with age, and leads to airway damage, a key driver of respiratory failure in CF (10). Although not used in the clinical management of individual patients, markers of airway inflammation provide very useful information in terms of airway disease activity and response to therapies. Several studies have described the utility of cytokines such as IL-8, IL-6, IL-1 β , matrix metallproteases (MMPs) and neutrophil products such as neutrophil elastase (NE)(11, 12). In CF, disruption of the protease-antiprotease balance has been demonstrated to be established in some individuals within the first year of life(3, 8, 9). Work to date suggests an association between NE, MMP-9 and bronchiectasis and disease severity in children with CF(6, 11, 13, 14). In addition, elevated NE activity is associated with *Pseudomonas aeruginosa* infection and destruction of host defence mechanisms(14, 15).

The introduction of triple combination therapies presents an ideal opportunity to collect, catalogue and analyse sputum samples for inflammatory markers prior to and after introduction, coupled with other key outcome measures relating to lung function and structure.

Nasal Inflammation

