The prevalence of CFLD ranges from 10–30%, depending on the criteria used to define liver disease(41-43). Currently there are two very similar consensus approaches to define CFLD(35, 44) which classify PWCF into three groups (i) CFLD; includes those with clinical evidence of liver disease (with or without portal hypertension), histological evidence on liver biopsy or radiological evidence of portal hypertension (ii) NSCFLD includes those with non-specific ultrasound or biochemical evidence of liver disease who do not fulfill criteria for CFLD, and (iii) those with no evidence of liver disease. When a diagnosis is established there are no clinical indicators that predict disease progression. More importantly, there is no effective intervention for prevention or treatment of established disease until liver transplantation for end-stage liver failure(35, 37).

In clinical trials, CFTR modulator drugs have been shown to be associated with elevation of liver transaminases, at times leading to cessation of treatment, temporarily in most instances. Little is understood about this or the natural history of variations in transaminases in CF. The medium to long term implications of

P.I. [name]

alterations of transaminases with CFTR modulator therapy is also unclear. Weight gain in individuals on lvacaftor is significant, and predominantly related to fat mass(45), raising concerns about the development of hepatic steatosis, although a single reported case has demonstrated the opposite, an improvement in steatosis on commencement of lvacaftor(46). A structured approach to the reporting of ultrasound findings such as in this study will shed light on this.

CFTR Modulators

Ivacaftor, the first mainstream CFTR modulator (a potentiator) is licenced for use in children with CF aged one year and older with a gating mutation and leads to improvements in sweat chloride, pulmonary function, weight gain, quality of life and rate of decline in lung function (47-51). Interestingly, in children aged 1 to 5 years, Ivacaftor was associated with improvements in markers of pancreatic insufficiency on treatment (52). Ivacaftor is currently in clinical trials in infants from birth to one year, and if found to be safe, will be the first disease modifying treatment available to infants with CF from birth.

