Adverse Reaction (AR)	Any untoward and unintended response in a subject to an					
	investigational medicinal product which is related to any dose					
	administered to that subject.					
	This includes medication errors, uses outside of protocol					
	(including misuse and abuse of product)					
Important Medical	These events may jeopardise the subject or may require an					
Event	intervention to prevent one of the above					
	characteristics/consequences. Such events should also be					
	considered 'serious'.					
SUSAR	Suspected Unexpected Serious Adverse Reaction					
	A serious adverse reaction the nature and severity of which is					
	not consistent with the information about the medicinal product					
	in question set out:					
	(a) in the case of a product with a marketing authorization, in					
	the summary of product characteristics for that product,					
	(b) in the case of any other investigational medicinal product, in					
	the investigator's brochure relating to the trial in question.					

Recording adverse events

All AEs occurring during the study observed by the investigator or reported by the subject, whether or not attributed to the study medication, will be recorded on the Case Report Form and in the medical notes unless they are stated as non-reportable events, in which case they will not be recorded. AEs will be collected from the time of consent until the final study visit

Non-reportable adverse events

Certain clinical and laboratory events in cystic fibrosis have a high background incidence or are considered to be typical clinical features of cystic fibrosis and would not need to be reported. These include the following;

- Pulmonary exacerbations and hospitalizations due to pulmonary exacerbations.
- Clinical signs and symptoms commonly associated with pulmonary exacerbations (nasal congestion, nasal discharge, cough, sputum production, drop in lung function, wheeze, crackles, positive bacterial/fungal cultures)
- Clinical signs and symptoms commonly experienced by patients with CF in their normal daily routine (abdominal discomfort/distension, headaches, fatigue, malaise, clubbing, nasal polyps)
- Symptoms of known CF complications such as liver disease (rise in liver function tests), diabetes, sinusitis, constipation and distal intestinal obstruction syndrome (DIOS)

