NOTE: Any of the above events deemed by the clinicians/ study investigators to be possibly related to the study drug or occurring to a disproportionate degree should be reported as an adverse event/serious adverse event.

Adverse Events of Special Interest

-Influenza is an adverse event of special interest, consistent with the risk management plan for Kaftrio. Occurrence of Influenza will be recorded as an adverse event or serious adverse event in every subject.

Assessments of Adverse Events

Each adverse event will be assessed for the following criteria:

Severity

Category	Definition
Mild	The adverse event does not interfere with the subject's daily routine, and does not require intervention; it causes slight discomfort
Moderate	The adverse event interferes with some aspects of the subject's routine, or requires intervention, but is not damaging to health; it causes moderate discomfort
Severe	The adverse event results in alteration, discomfort or disability which is clearly damaging to health

Causality

The assessment of relationship of adverse events to the administration of IMP is a clinical decision based on all available information at the time of the completion of the case report form. The following categories will be used to define the causality of the adverse event:

Category	Definition
Definitely:	There is clear evidence to suggest a causal relationship, and other possible contributing factors can be ruled out.
Probably:	There is evidence to suggest a causal relationship, and the influence of other factors is unlikely
Possibly	There is some evidence to suggest a causal relationship (e.g. the event occurred within a reasonable time after administration of the trial medication). However, the influence of other factors may have contributed to the event (e.g. the patient's clinical condition, other concomitant events).
Unlikely	There is little evidence to suggest there is a causal relationship (e.g. the event did not occur within a reasonable time after administration of the trial medication). There is another reasonable explanation for the event (e.g. the patient's clinical condition, other concomitant treatments).
Not related	There is no evidence of any causal relationship.
Not Assessable	Unable to assess on information available.

Expectedness

Category	Definition
Expected	An adverse event that is classed in nature as serious and which is consistent with the information about the IMP listed in the SmPC

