Unexpected	An adverse event that is classed in nature as serious and which is not consistent with the information about the IMP listed in the Investigator Brochure (or SmPC if Licensed IMP)

The reference document to be used by the Sponsor (RCSI) to assess expectedness of the event against the IMP is the SmPC for:

ETI (EU marketing authorisation number EU/1/20/1468/001)

Seriousness

The Principal Investigator (PI) should make an assessment of seriousness as defined below:

A Serious Adverse Event (SAE) is any adverse event that:

- results in death,
- is life-threatening,
- requires hospitalisation or prolongation of existing hospitalisation,
- results in persistent or significant disability or incapacity, or
- consists of a congenital anomaly or birth defect
- is considered to be an important medical event (in the opinion of the investigator)*

* These events may jeopardise the subject or may require an intervention to prevent one of the above characteristics/consequences. Such events should also be considered 'serious'.

Procedures for recording and reporting Serious Adverse Events

All serious adverse events will be recorded by the site staff in the hospital notes, on the CRF, and the sponsor's SAE form.

All serious adverse events will need to be reported to the sponsor on a SAE form unless they fall under the category of non-reportable adverse events.

The Principal Investigator (PI) or appropriate designee is responsible for capturing SAEs on the appropriate trial specific SAE forms and reporting all SAEs to RCSI Pharmacovigilance ([contact]) within 24 hours of first becoming aware of the event (as per the RCSI Sponsor SOP on Expedited Safety Reporting). It is important to note that in the event that an SAE was not previously documented as an AE, the PI or designee must also fill out an AE form in junction with an SAE form.

SAEs will be collected from consent until the final study visit. SAEs that are related to the investigational drug and continue beyond the normal collection period (i.e., are ongoing at the time a subject exits the study) will be followed until resolution or until stabilized with sequelae. SAEs that begin after the subject's participation in the study is complete, but that the PI considers to be related to study drug, may be reported at any time. Reporting to the sponsor will be completed as per the Sponsor's Expedited Safety Reporting SOP.

Reporting SUSARs

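### The safety-reporting exemption does not stop at fatal or life-threatening events, and the protocol contradicts itself on whether exempt serious events are recorded and reported

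*Protocol*

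**What the plan says.** The relevant rules are spread over several adjoining headings of the protocol's safety section.

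- *Recording adverse events*: adverse events go on the case report form and in the medical notes "unless they are stated as non-reportable events, in which case they will not be recorded".
- *Non-reportable adverse events*: the first listed item is "Pulmonary exacerbations and hospitalizations due to pulmonary exacerbations". A later item reads "Symptoms of known CF complications such as liver disease (rise in liver function tests", and goes on to other complications. No item is limited by severity or outcome.
- The note closing that list restores reporting for a listed event deemed "to be possibly related to the study drug or occurring to a disproportionate degree should be reported as an adverse event/serious adverse event".
- *Seriousness*: an event that is fatal or life-threatening is a serious adverse event, as is one requiring hospitalisation.
- *Procedures for recording and reporting Serious Adverse Events*: the first sentence is "All serious adverse events will be recorded by the site staff in the hospital notes, on the CRF, and the sponsor's SAE form". The second says that serious events "will need to be reported to the sponsor on a SAE form unless they fall under the category of non-reportable adverse events". The next paragraph makes the site investigator responsible for reporting all SAEs to the sponsor's pharmacovigilance function within 24 hours.
- *Reporting SUSARs*: fatal or life-threatening SUSARs have a 7-day limit. This is the only rule specific to such outcomes.

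**The concern.** Exempting routine exacerbations is understandable in cystic fibrosis, where they are frequent. The difficulty is that the exemption is defined by type of event and never by outcome, so on its wording it extends to an exacerbation that kills or nearly kills a participant.

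The protocol's own background shows that lung-related death is the one to expect here: "The most common cause of death in people with CF is respiratory failure associated with progressive CF lung disease". An event that does not reach the sponsor on an SAE form is not available, by that route, for sponsor assessment as a possible SUSAR or for the count of serious events. The study follows treated participants without a concurrent control group, so the site's opinion on relatedness is a weak filter for deaths. If sites also read the conflicting sentences differently, the serious-event count would depend partly on where a participant was treated.

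**Working it through.** No arithmetic applies, and the protocol states no figure to reproduce. The check is to take one case through every rule: a participant dies of a pulmonary exacerbation that the site judges unrelated to the study drug.

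| Rule | Result for this case |
|---|---|
| *Seriousness* | It is an SAE |
| *Non-reportable adverse events* | It is a listed event; no outcome limit |
| Note to that list, first trigger (possibly related) | Not met, by assumption |
| Note to that list, second trigger (disproportionate degree) | Undetermined; the term is undefined and death is not said to meet it |
| *Recording adverse events* | Not recorded |
| *Procedures*, first sentence | Recorded in the notes, on the CRF and on the SAE form |
| *Procedures*, second sentence | Need not be reported to the sponsor |
| *Procedures*, 24-hour duty | Reported, because it covers all SAEs |
| *Reporting SUSARs* | Does not apply; a SUSAR is a suspected reaction |

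**Does the list reach serious events at all?** Yes. It names hospitalisation for an exacerbation, and hospitalisation is itself a seriousness criterion. The second sentence of *Procedures* also applies the exemption to serious events in terms.

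**Recording.** Two rules give opposite answers. Nothing says which prevails.

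**Reporting.** The exemption and the 24-hour duty also differ. If the duty to report all SAEs prevailed, the exemption sentence would have no effect. The more natural reading is that the exemption qualifies the duty. On that reading the death need not be reported unless someone at the site invokes the second trigger.

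**Is the exempt category itself bounded?** No. Under *Definition of Exacerbation* the protocol deliberately declines to define an exacerbation. Whether a terminal respiratory illness counts as one is left to each site.

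**Is there another stated route for deaths?** Mortality is not in the outcome list under *Primary and Secondary Outcomes*. Table 14 has an adverse event check but no separate item for death.

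**The case against.** The strongest reply is that the protocol already requires all SAEs to be recorded and all to be reported within 24 hours. In addition, the note to the list offers two alternative triggers, open to clinicians as well as investigators. Possible relatedness is a low bar, and a fatal exacerbation is an obvious candidate for disproportionate degree. Sponsor procedures that are not shown may also cover deaths. This stands to the extent that under-reporting is a risk and not a certainty. It does not remove the defect, because the safeguards contradict other sentences or rest on an undefined term.

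A reader might draw several stronger conclusions that the text does not support.

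- *That such deaths would go unrecorded.* The recording rule in *Procedures* says the opposite of the one in *Recording adverse events*. This is a contradiction, not a settled rule of non-recording.
- *That deaths from CF liver disease are exempt.* The list covers symptoms of complications, with a rise in liver function tests as the liver example. Liver failure and liver death are not named.
- *That every respiratory death is exempt.* The list names exacerbations, their hospitalisations and common signs. Respiratory failure from progressive disease is not an item, although the boundary is blurred when exacerbation is undefined.
- *That the earlier Irish liver-disease cohort gives the size of the problem.* There, 9 of 18 deaths in people with CF liver disease were hepatic and 8 of 18 pulmonary. The hepatic deaths match no listed item, and how many pulmonary deaths were exacerbations is not stated. These counts show which organs were involved and do not estimate an undercount.
- *That rises in liver function tests must come off the list.* The background does say that "CFTR modulator drugs have been shown to be associated with elevation of liver transaminases, at times leading to cessation of treatment". But under *Liver Function Test* the protocol collects these results and compares elevations, by multiple of the upper limit of normal, with each participant's earlier values and with historic controls. Listing them separately as adverse events is a matter of preference.

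**Conclusion.** The point holds in a limited form. The exemption has no exception for fatal or life-threatening outcomes. A death or life-threatening event from a pulmonary exacerbation that is judged unrelated and not disproportionate need not be reported to the sponsor as an SAE. Separately, the protocol gives opposite instructions on recording listed serious events and inconsistent ones on reporting them, so site practice could differ and serious events could be undercounted.

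The size is unknown. The protocol gives no expected rate of fatal or life-threatening exacerbations in this cohort, and none can be derived from its figures. The conclusion rests on the protocol wording alone and assumes that the sponsor's expedited reporting procedure, which is not shown, does not override it.

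**What to change.** 1. Under *Recording adverse events* / *Non-reportable adverse events*, and again under *Procedures for recording and reporting Serious Adverse Events*, state that the non-reportable exemption does not apply to fatal or life-threatening events. These are recorded and reported as SAEs whatever the attributed cause.
2. Reconcile the three places that govern listed serious events: the non-recording clause, the note with its two triggers, and the *Procedures* sentences on recording, exemption and 24-hour reporting. For a listed event that is serious but neither fatal nor life-threatening, such as a routine admission for an exacerbation, say plainly whether it is recorded and whether it is sent to the sponsor.
3. As part of that reconciliation, define the disproportionate-degree trigger or delete it.

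The cost is a few sentences and a small number of extra SAE forms. Routine exacerbations can remain exempt, so the purpose of the list is kept.
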